### 3. Introduction and Background:

**Background:** Prior to ED RSI, it is necessary to provide patients with pre-oxygenation to displace nitrogen from the alveoli and replace it with oxygen. This allows the patient to maintain their arterial oxygen saturation during the apneic period of RSI. Patients who experience hypoxia during RSI are at higher risk for serious morbidity and mortality. Techniques commonly employed to pre-oxygenate Emergency Department (ED) patients undergoing RSI include high flow oxygen via a non-rebreather mask (NRBM), a self-inflating bag-valve mask (BVM), or non-invasive ventilation (NIV). However, there are currently no studies that explore how to assess the quality of a patient's pre-oxygenation in real time prior to intubation.

Several recent studies that have assessed the use of single breath end-tidal oxygen to assess the effectiveness of various oxygenation strategies. Typically, healthy volunteers are placed on 2 to 3 minutes of a certain pre-oxygenation strategy followed by exhalation of a single

breath into an end-tidal oxygen sensor. Higher end-tidal oxygen measurements are used as a marker for pre-oxygenation with higher percentages indicating more complete pre-oxygenation.

A goal EtO2 reading of 90% is typically used to indicate maximal pre-oxygenation. However, this method of assessing pre-oxygenation would be impractical in actual ED patients who are critically ill and may not be able to fully participate in such a measurement. In addition, discontinuing a pre-oxygenation method to obtain a single breath EtO2 reading would be unethical as it would interfere with proper pre-oxygenation in a critically ill patient. A better method would be to examine end-tidal oxygen measurements from patients in real-time as they are being pre-oxygenated. This study will examine the use of a real time nasal cannula EtO2 sensor as compared to the gold standard of a single breath exhalation into a static sensor.

## **Introduction**

We hypothesize that end-tidal oxygen (EtO2) could be continuously and reliably measured using a nasal cannula with a gas sampling line that is typically used to measure end-tidal CO2 (EtCO2) during pre-oxygenation in healthy volunteers. However, it is possible that high flows of oxygen that would be typically required for pre-oxygenation could distort patient measurements when placed underneath the oxygen mask. To our knowledge, no studies have examined this technique.

Use of the EtO2 real time reading from a nasal cannula could lead to improved pre-oxygenation for ED patients undergoing RSI by allowing clinicians to gauge the completeness of pre-oxygenation prior to starting the intubation procedure. Clinically, if a patient has a low EtO2 or ORI reading, this could prompt clinicians to delay the procedure until the patient can be better pre-oxygenated. This could lead to improved patient safety by decreasing the incidence of hypoxia during the intubation procedure that can lead to significant morbidity and mortality. Conversely, if the EtO2 is already at 90% or greater, the clinician may be able to start the intubation procedure sooner and not delay other critical interventions while waiting to further pre-oxygenate the patient.

### **3. Objectives:**

Primary Objective: In healthy volunteers, how well does a real time nasal cannula EtO2 sensor correlate with a single breath exhaled EtO2 measurement?

### **4. Study design and methods:**

#### **Study Procedure**

After screening procedures, participants will be asked to self report age, gender, height, and weight. Each participant will then perform a single breath EtO2 measurement to determine their own individual room air EtO2 measurement. They will also have a baseline measurement taken by the EtO2 nasal cannula sensor. Subjects will then be fitted for an appropriately sized non-invasive ventilator mask. Prior to the start of the study procedure, a nasal cannula EtO2 sensor will be placed on the participant's face with the non-invasive mask overlying the sensor. Participants will be randomized into each study arm after enrollment: the NRBM arm and the

NIV arm. Each participant will participate in the following treatment sequence. In addition to the study arm allocation, participants will be randomized to the order of their treatment sequence. After each treatment is completed, the participant will perform a single breath exhalation into a standard FeO2 sensor.

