Real Time Assessment of Pre-oxygenation Utilizing End-tidal Oxygen Measurements versus Single Breath End-Tidal Oxygen Measurements in Healthy Volunteers

Short Title: Pre-oxygenation with Real Time End-tidal Oxygen Measurements versus Single Breath Measurements

Principal Investigator: [name]

Sponsors: None

Protocol Version 6  
March 20, 2025

NCT03840486

1. External (non-Emory) Collaborators: Not applicable
2. Precis/Abstract: A brief (usually 400 words or fewer) description of the study objectives, population, design, and outcome measures

Patients in the Emergency Department (ED) undergoing Rapid Sequence Intubation (RSI) are at risk for serious morbidity and mortality. In order to provide oxygen during the apneic period, it is common practice to provide pre-oxygenation prior to the start of the procedure with high flows of oxygen. Different methods of pre-oxygenation have been studied by taking a single breath end-tidal oxygen (EtO2) measurement with higher levels indicating more complete pre-oxygenation. However, there has not been any research examining methods of determining the quality of pre-oxygenation in real time.

This study examines the performance of a nasal cannula EtO2 measurement as compared to the gold standard of single breath end-tidal oxygen measurements in healthy volunteers. Study subjects will be placed on either a NRBM at different flow rates (15 LPM, 35 LPM, or Flush rate at 55 LPM) or a non-invasive ventilator facemask at various fractions of inspired oxygen levels (40%, 70% and 100%) for separate trials of 3 minutes at each flow rate or FiO2. At the end of each intervention, study subjects will perform a single breath end-tidal oxygen measurement by exhaling fully into a tube attached to an EtO2 sensor. In addition, a fourth trial arm will be done for both the NRBM and the NIV subjects that will correlate maximal readings from the real time EtO2 nasal cannula at the moment those maximal readings are obtained. The primary outcome will be the degree of correlation between real time EtO2 measurements (at the end of the three minute trial) and a single breath end-tidal oxygen measurement as measured by the k correlation coefficient, as measured for each trial. The secondary outcome will be the correlation of EtO2 between the nasal cannula sensor and the single breath sensor once stabilized at maximal readings.

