**Group 2: NIV arm**

#1 NIV at 40% FiO2 for 3 minutes

#2 NIV at 70% FiO2 for 3 minutes

#3 NIV at 100% FiO2 for 3 minutes, the maximal reading at the end of this trial will be recorded, then the study subject will be allowed to rest until their EtO2 returns to their baseline, then they will be placed back on NIV at 100% FiO2, allowed to rise to the maximal reading of the previous step, then do a single breath exhaled EtO2 measurement

After each trial for #1 and #2 in each study arm, the study participants will be allowed to rest while breathing room air. Prior to the start of the next trial, each participant will perform a single breath EtO2 measurement to ensure they have returned to their baseline measurement. If the measurement is determined to be above their baseline, they will be allowed to rest until their single breath EtO2 measurement returns to its pre-intervention baseline. For trial #3 in each arm, the protocol will be followed as above so that the maximal reading can first be obtained to allow the completion of arm #3.

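### Only correlations are planned: with no analysis of the nasal minus single-breath difference, flow-related bias would not be estimated and the paired room-air readings go unused

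*Combined protocol and SAP*

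**What the plan says.** Study Procedure collects a pair of readings on room air before the mask is fitted. For the single breath: "Each participant will then perform a single breath EtO 2 measurement to determine their own individual room air EtO 2 measurement". For the cannula: "They will also have a baseline measurement taken by the EtO 2 nasal cannula sensor". Each participant then goes through three settings in randomised order: 15, 35 and 55 LPM in the NRBM arm, or FiO2 40, 70 and 100% in the NIV arm.

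The Introduction gives a reason to doubt the cannula: "high flows of oxygen that would be typically required for pre-oxygenation could distort patient measurements when placed underneath the oxygen mask".

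The Precis/Abstract defines the outcomes. The primary is a correlation at the end of the three minutes, "as measured by the k correlation coefficient, as measured for each trial". For the secondary: "The secondary outcome will be the correlation of EtO 2 between the nasal cannula sensor and the single breath sensor once stabilized at maximal readings". The Objectives section also asks only about correlation.

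The Statistical Analysis section covers power, exclusion of incomplete participants and imputation. It names no model, no paired difference, no contrast across settings and no baseline term. The explicit use of the single-breath baseline is procedural, as a washout check: "each participant will perform a single breath EtO 2 measurement to ensure they have returned to their baseline measurement". The rest step inside trial #3 also refers to baseline, without naming the sensor.

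**The concern.** The Introduction expects clinicians to act on the absolute cannula value, with 90% as the reference. A cannula that reads a few points high or low matters for that use even if it ranks participants perfectly. A correlation computed separately for each trial does not measure that error.

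The design holds what is needed to measure it: both sensors in the same person, at three settings, plus a pair at zero flow. With only the stated outcomes, two results would be lost. A bias that grows with flow would not be estimated. A shift of the same size at all three flows would not be told from a cannula that always differs from the single breath by that amount.

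**Working it through.** **Inputs from the plan.** EtO2 SD 6.8, difference of interest 5 points, level 0.0085, power 80%, 52 per arm (Power calculation); flows 15, 35 and 55 LPM (Group 1).

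**Assumed, because the plan gives no figure.** SD of the between-sensor difference 3 points (range 2 to 5); mean EtO2 15.5% on room air and 60, 70 and 85% at the three flows.

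**The plan's own figures.**
- Sidak level: 1 − 0.95^(1/6) = 0.0085. Reproduced.
- Enrolment: 104 / 0.90 = 115.6, so 116. Reproduced.
- Apnea equivalent: 5% × 2,400 ml = 120 ml; 120 / 250 = 0.48 min, about 29 seconds. Agrees with the stated 30.
- 52 per arm: not reproduced. A two-sided two-sample comparison needs 45 (normal approximation) or 47 (t test) per arm, and 52 gives 85.4% power (t test). The section does not say what is compared. The gap is conservative and does not affect this point.

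**Step 1: what a correlation sees.** Write the cannula reading as single breath + shift + noise. Then r = 6.8 / √(6.8² + 3²) = 6.8 / 7.43 = 0.91. The shift does not enter. Simulation with 52 participants gave:

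| Scenario | Correlation at 15 / 35 / 55 LPM | Mean difference at 15 / 35 / 55 LPM | Room-air difference |
|---|---|---|---|
| Fixed offset of 5 | 0.91 / 0.91 / 0.91 | 5.0 / 5.0 / 5.0 | 5.0 |
| Shift of 5 at every flow | 0.91 / 0.91 / 0.91 | 5.0 / 5.0 / 5.0 | 0.0 |
| Shift of 2, 4, 6 | 0.91 / 0.91 / 0.91 | 2.0 / 4.0 / 6.0 | 0.0 |
| Extra random noise, SD 0, 4, 8 | 0.91 / 0.80 / 0.62 | 0.0 / 0.0 / 0.0 | 0.0 |

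The first three rows are identical in correlation. The graded shift shows in the mean differences with no baseline at all. Only the first two rows need the room-air pair to be told apart.

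**Step 2: what the room-air pair cannot do.** Suppose the cannula reads 6% too high in proportion, with no flow effect. The room-air difference is 0.06 × 15.5 = 0.9. The trial differences are 0.06 × 60 = 3.6, 0.06 × 70 = 4.2 and 0.06 × 85 = 5.1. Subtracting room air leaves 2.7, 3.3 and 4.2 points that would wrongly be put down to flow. The contrast of 55 with 15 LPM also picks up 5.1 − 3.6 = 1.5 points, because EtO2 rises with flow in this example.

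**Step 3: precision available.** For the difference between two conditions in the same 52 people, SE = s × √(2/52), if the two between-sensor differences have equal SD s and are independent. The detectable contrast is (2.63 + 0.84) × SE.

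| s (assumed) | SE | Detectable contrast |
|---|---|---|
| 2 | 0.39 | 1.4 |
| 3 | 0.59 | 2.0 |
| 5 | 0.98 | 3.4 |

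All are below the plan's 5 points. Positive correlation between conditions would make them smaller.

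**The case against.** The strongest reply is that the stated objective is how well the sensors correlate, not why they differ, and that the plan does so. That is fair. The planned correlations are not invalid, and this point asks for an addition beside them.

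Second, the Power calculation speaks of a 5% difference in EtO2 and six tests, so some analysis of differences may be intended. It is not defined anywhere, so it cannot fill the gap.

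Third, a reader might infer that the plan cannot separate flow distortion from a fixed offset at all. The documents do not support that. An offset leaves a Pearson-type correlation unchanged, so a fall in correlation from 15 to 55 LPM could not come from an offset, although a restricted range at high EtO2 could also cause it. Graded bias is present in the within-person data without any room-air reading. The coefficient called k is also undefined; an agreement-type coefficient would respond to an offset, though without showing its cause.

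Fourth, a reader might expect baseline adjustment to tighten the estimates by √(1 − r²), that is 0.95, 0.87 or 0.71 for r = 0.3, 0.5 or 0.7. That formula suits a comparison between groups. It does not tighten a mean difference within an arm. A baseline covariate with a common slope cancels from within-person contrasts between settings. Change from room air has SE ratio √(2(1 − r)) = 1.18, 1.00 or 0.77 against the unadjusted difference, so it can be worse. The documents give no r.

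Finally, in the NIV arm the varied factor is FiO2, so the flow argument applies directly only to the NRBM arm. This stands.

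**Conclusion.** The point holds in a limited form. The plan specifies only correlations. It has no analysis of the between-sensor difference, no within-person contrast across settings and no analytic use of the room-air pair, although it raises flow distortion itself. If k is a Pearson-type coefficient, a 5-point shift leaves it at 0.91 whether the shift is fixed, common to all flows or replaced by one that grows from 2 to 6 points. These figures rest on an assumed between-sensor SD of 3 points.

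What is gained is an estimate of bias and of its change with flow, not greater precision. Room air is an imperfect zero-flow reference: by the order of Study Procedure it is taken without the mask, and it is taken at low EtO2. It therefore removes an additive offset only, and mask effect and gain error remain mixed with flow. The change should be made, but the planned correlations can stand as they are.

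**What to change.** Beside the planned correlations, pre-specify one linear mixed model of the nasal minus single-breath difference:
- Room air enters as a zero-flow reference condition. Arm-by-setting and trial position are fixed effects, and participant is a random effect. Room air always comes first, so position applies to the oxygen trials only.
- Report the mean difference and limits of agreement at each setting.
- Report the within-person contrast across 15, 35 and 55 LPM in the NRBM arm, and across FiO2 in the NIV arm. The NIV contrast may help to judge error that depends on EtO2 level.
- Report the change from room air as supportive only, and state that this pair is taken without the mask and at low EtO2, so that it removes only an additive offset.

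Define the k coefficient in the same edit. The cost is analysis text and one model; all the data are already planned.

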**Group 1: NRBm Arm**

#1 NRBm at 15 LPM for 3 minutes

#2 NRBm at 35 LPM for 3 minutes

#3 NRBm at flush rate (55 LPM) for 3 minutes, the maximal reading at the end of this trial will be recorded, then the study subject will be allowed to rest until their EtO2 returns to their baseline, then they will be placed back on NRBm at flush rate, allowed to rise to the maximal reading of the previous step, then do a single breath exhaled EtO2 measurement

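### Does the loose wording of trial #3 leave the secondary outcome undefined, or the primary outcome without a single breath at the highest setting?

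*Combined protocol and SAP*

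**What the plan says.** The document is a combined protocol and SAP. Four places bear on trial #3.

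- **Section 2, Precis/Abstract.** A breath follows every exposure: "At the end of each intervention, study subjects will perform a single breath end-tidal oxygen measurement". In addition, "a fourth trial arm will be done for both the NRBM and the NIV subjects", with the cannula and single breath compared "at the moment those maximal readings are obtained". The primary outcome is the end-of-three-minutes correlation, "as measured for each trial". The secondary outcome is the correlation "once stabilized at maximal readings".
- **Section 4, Study Procedure.** The general rule is repeated: "After each treatment is completed, the participant will perform a single breath exhalation".
- **Group 1: NRBm Arm and Group 2: NIV arm.** Items #1 and #2 give only a setting and a duration. In item #3, after 3 minutes, "the maximal reading at the end of this trial will be recorded". The participant then rests to baseline, is re-exposed, and is "allowed to rise to the maximal reading of the previous step, then do a single breath exhaled" into the sensor. The paragraph closing Group 2 explains that the first run supplies the maximum that the second run needs.
- **Statistical Analysis.** The Power calculation section counts six tests at a Sidak level of 0.0085 and drops the data of participants unable to finish the protocol. The Missing Data section provides for multiple imputation when much is missing.

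**The concern.** Three things look wrong on a first reading.

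1. **Timing.** Reaching a value recorded in an earlier exposure is not the same as having settled at a plateau. The Precis/Abstract uses both ideas, and no stability criterion, dwell time or tolerance is given. The target itself might be read as the peak or as the last value of the first run.
2. **No rule for failure to regain the maximum.** Such a participant has no clearly defined secondary pair. If staff treated this as not finishing the protocol, the exclusion rule would also remove that person's valid primary pairs, because of a reading from the device being evaluated.
3. **The primary breath in #3.** The arm lists go from recording the maximum straight to rest. If no breath is taken there, the primary outcome has no end-of-three-minutes pair at flush rate or at 100% FiO2, the settings closest to actual pre-oxygenation practice.

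The third matters most, because it touches the primary outcome. The screen video is deleted after transcription (Confidentiality), so a reading that was not transcribed could not be recovered later.

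**Working it through.** **What is at stake in counts.** Inputs: 104 participants with complete data and a maximum enrolment of 116 (Participant selection; Power calculation).

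| Reading of #3 | Post-exposure breaths | End-of-three-minutes primary pairs |
|---|---|---|
| Breath after the first run and after re-exposure | 104 × 4 = 416 | 104 × 3 = 312 |
| Breath after re-exposure only | 104 × 3 = 312 | 104 × 2 = 208 |

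The difference is 312 − 208 = 104 pairs, and 104/312 = 33.3%.

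**Which reading does the text support?** The second row applies the Study Procedure's general rule to #1 and #2 but withholds it from #3. Items #1 and #2 in the arm lists name no end-of-trial breath either. They rely wholly on the general rule, so silence in #3 is not evidence that the rule stops there. The re-exposure breath is written out because it is the extra one, which matches the Precis/Abstract's description of an added fourth trial. The primary outcome is also defined for every trial.

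**The count of six tests.** The plan's level is reproduced: 1 − (1 − 0.05)^(1/6) = 0.00851, stated as 0.0085. Three settings × two arms gives 6. Two settings × two arms plus one re-exposure × two arms also gives 4 + 2 = 6, so the number alone does not decide. The second sum has to leave the highest setting out of a primary outcome defined for every trial. The count therefore leans towards a breath after the first run of #3, but the section does not name the six tests.

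**Timing of the secondary reading.** How far the 3-minute level lies below plateau is not in the documents. As an assumption, take an exponential rise from 16 to 85 with time constant τ. The gap at 180 s is (85 − 16) × exp(−180/τ):

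- τ = 30 s: 69 × exp(−6) = 0.2 points
- τ = 45 s: 69 × exp(−4) = 1.3 points
- τ = 60 s: 69 × exp(−3) = 3.4 points

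Under these assumptions the gap is below the 5-point difference used in the Power calculation. The two descriptions may or may not coincide exactly. Either way, the abstract's timing places the breath at the moment the maximum is obtained, so the two readings are contemporaneous. As for peak or final value, the arm lists locate the reading at the end of the trial. On a rising curve the two differ only by breath-to-breath variation.

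**Failure to regain the maximum.** If a participant were classed as incomplete, 3 primary pairs would be lost for 1 uncertain secondary pair. That person would use one of 116 − 104 = 12 allowed losses (12/116 = 10.3%). How often this would happen cannot be derived from the documents, and any simulated rate would only reflect its assumed inputs.

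**The case for a change.** The strongest case for a change is that staff work from the step-by-step lists, not from an abstract. Those lists go from the maximum to rest and then to one breath, and the closing sentence of Group 2 presents the first run as a means of obtaining the target. Two teams could follow the text in good faith and collect different data. No section names the event of not regaining the maximum, and the two nearest rules pull apart: one excludes, the other imputes. Clarifying a few sentences would cost almost nothing.

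Part of this stands. The closing sentence of Group 2 is awkward. The abstract counts the re-exposure as a fourth trial, while the arm lists fold it into #3. The event is not addressed.

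The step from there to harm is weaker. The Study Procedure sits in the same section as the lists and governs them. Risks and Discomforts and the withdrawal text under Exclusion criteria tie stopping early mainly to mask intolerance. Treating someone who wore the mask throughout as unable to finish is a strained reading. Recruitment to 104 complete data sets protects the sample size for up to 12 losses. It would not undo selection if the strained reading were applied, but nothing suggests that it would be. The data form is not among the documents, so it cannot be said to lack the readings.

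**Conclusion.** No change follows. This is uneven wording plus a small gap that competent staff and analysts would fill sensibly. Following the Precis/Abstract and the Study Procedure, they would take a breath after each 3-minute exposure, giving 312 primary pairs, and one further breath at re-exposure for the secondary outcome. The loss of 104 pairs arises only under the less natural reading. The secondary timing has a workable meaning: the breath is taken when the cannula reaches its earlier end-of-trial maximum and is paired with the reading at that moment. A participant who does not regain that maximum leaves a question over one secondary pair, with no good reason to discard the primary ones.

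The conclusion rests on two assumptions: that the general breath rule applies to #3 as it does to #1 and #2, and that non-completion means stopping early. The text supports both without stating either outright. No material effect on the primary or secondary correlation has been shown, and choosing between the two descriptions of the secondary timing offers no demonstrated gain.
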